12. ADDITIONAL GENETICS STUDY

12.1 The role of filaggrin gene mutations as a predictor of treatment response

Mutations in the gene encoding the skin barrier protein filaggrin have recently been shown to strongly predispose to eczema. Reduced filaggrin activity is associated with an abnormally dry skin and defective skin barrier. It is estimated that up to 50% of children with eczema may carry one or two mutations in the gene encoding filaggrin, which has the gene symbol *FLG* ¹⁸. Individuals carrying one null-allele for filaggrin make only 50% of the normal amount of filaggrin. Often these individuals have a mild form of ichthyosis vulgaris (a very dry skin) and are at risk for eczema. Individuals who have two null-alleles make no filaggrin and have a more severe form of ichthyosis vulgaris and are at greater risk of eczema ^{19,20}.

In light of this breakthrough in understanding eczema, we have formed collaborative links with the research team that first reported this association (lead by [name] at the Human Genetics Unit, University of Dundee). We plan to include filaggrin status as a possible predictor of treatment response in the current study. The mechanism of action by which water softeners improve eczema is currently unclear. Nevertheless, it seems intuitive to consider the possibility that a gene associated with dry skin may play an important role in predicting why some people with eczema are more affected by hard water than others.

For the sub-group analysis, study participants will be categorised into two groups according to filaggrin status:

Group 1: *FLG* +/+ (wild type) – control cohort

Group 2: *FLG* +/- (heterozygous for *FLG* null allele) and *FLG* -/- (homozygous for *FLG* null alleles)

This work will refine the phenotypic characteristics of filaggrin-deficient eczema, and will assess whether filaggrin is an important predictive factor in determining treatment

success.

12.2 Methodology

To determine filaggrin status it will be necessary to obtain DNA from individuals entering the study. Following written informed consent, participants will be asked to provide a saliva sample at enrolment (or at their 4-week clinic appointment, if more practical). If children are unable to spit into the container, swabs taken from inside the cheek will be used to collect the sample.

Sample containers will be identified using the designated study number and date of birth only. Personal contact details will be kept by the Trial Manager and will not be transferred to the laboratory researchers.

The containers will be shipped to the Human Genetics Unit, University of Dundee. DNA will be extracted by standard techniques and *FLG* genotyping for the common null-alleles will be carried out according to published protocols ¹⁹. Samples will be kept in Dundee for future testing for genes associated with atopic eczema if new techniques become available.

FLG genotype status will be recorded and returned to the Centre of Evidence Based Dermatology in Nottingham, again using the study number and date of birth.

12.3 Written informed consent

Parents and participants will be offered the possibility of opting out of this part of the study. No participant will be enrolled until informed consent has been gained.

12.4 Sample size

The sample size for the main trial is based on the ability to detect at least a 20% difference in disease severity between the two groups (water softener versus usual eczema care). In order to ensure that sufficient power is available for the planned sub group analysis, further sample size calculations have been performed.

Assuming that the presence of at least one mutation in the gene encoding filaggrin results in improved treatment response, a total of 90 children with at least one such mutation would be sufficient to detect a 30% difference between the treatment groups in the primary outcome (disease severity), with 80% power and a significance level of 5% (s.d = 10). Allowing for 20% drop out means that 120 (39% of the children recruited) would need to carry the gene mutation. For 90% power, this figure would be 145 (47%) children. This is in line with previous published findings which suggest that the gene may be present in up to 50% of eczema sufferers 19 , although this varies according to ethnic group 21,22 .

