10.2 Sample Size estimate

Sample size estimates are based on other published data relating to the use of SASSAD in patients recruited in secondary care¹⁵, ⁵. Based on a minimum clinically relevant difference of 20% in the change in SASSAD score between the 2 groups, and assuming a mean baseline SASSAD score of 20 with a standard deviation in change scores of 10 ¹⁵, a sample size of 310 children will provide 90% power, assuming a significance level of 5% and attrition rate of 15% (see planned interventions section). Sample size estimates based on the results of the pilot study, support this sample size estimate.

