7. PLANNED SUBGROUP ANALYSES

A sub-group analysis will be conducted based on the presence or absence of mutations on the filaggrin gene (collected using spit samples). Mutations on the filaggrin gene have been associated with dry skin and may therefore be a useful predictor of treatment success. The planned subgroup analysis will only be performed on the primary outcome of change in SASSAD score. The p-value for the interaction will be reported.

Assuming that the presence of at least one mutation in the gene encoding filaggrin results in improved treatment response, a total of 90 children with at least one such mutation would be sufficient to detect a 30% difference between the treatment groups in the primary outcome, with 80% power, 5% significance (2 sided) and a standard deviation of 10. Allowing for a 20% drop out means that 120 children would need to carry the gene mutation. For 90% power this figure would be 145.

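### The filaggrin subgroup is sized for the treatment difference within mutation carriers, but the SAP tests the treatment-by-filaggrin interaction, for which no power is stated and power is well below 80%

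*Combined protocol and SAP*

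**What the plan says.** Protocol 12.4 (Sample size, genetics study) gives the purpose of the calculation: "In order to ensure that sufficient power is available for the planned sub group analysis, further sample size calculations have been performed". It then states that "a total of 90 children with at least one such mutation would be sufficient to detect a 30% difference between the treatment groups", "with 80% power and a significance level of 5% (s.d = 10"). After a 20% drop-out allowance it asks for 120 carriers (39% of those recruited), or 145 (47%) for 90% power. It regards these shares as consistent with published carriage of up to 50%, and notes that carriage varies by ethnic group.

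Protocol 12.1 splits participants into wild type and carriers of one or two null alleles. Its aim is to learn whether filaggrin status predicts treatment success.

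SAP 7 restricts the subgroup analysis to change in SASSAD and names one inferential result: "The p-value for the interaction will be reported". Its next paragraph repeats the 90, 120 and 145 figures and adds that the test is two-sided.

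Neither document states an expected effect in non-carriers, an interaction effect size, or power for the interaction test.

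**The concern.** The calculation and the planned test address different quantities. The 90 children answer whether the softener works among carriers, and non-carriers do not enter that calculation. The subgroup question is whether the softener effect differs between carriers and non-carriers. That is a difference of two differences, so its variance is the sum of the variances in the two strata.

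What is at stake is the reading of the result. When a protocol says that power has been secured for this analysis, a non-significant interaction invites the conclusion that filaggrin does not matter. A test with the power shown below cannot support that conclusion. SAP 7 gives no rule for interpretation and promises a p-value without an estimate or interval.

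**Working it through.** **Inputs from the documents.** The main sample size sections (Protocol 10.2, SAP 4) work "assuming a mean baseline SASSAD score of 20" and take a "minimum clinically relevant difference of 20% in the change in SASSAD score between the 2 groups", so 20% is 4 points and 30% is 6 points. SD is 10, alpha 5% two-sided (SAP 7), allocation 1:1 (Protocol 8.3), and 310 are randomised. Loss is 20% in the subgroup calculation and 15% in the main one.

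**Step 1: reproduce the 90.** Normal approximation, per arm: 2 × (1.96 + 0.84)² × (10/6)² = 43.6, so 44 per arm and 88 in total. The exact t-test needs 45 per arm, total 90, with 80.4% power. The stated 90 therefore reproduces as a two-arm comparison within carriers.

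**Step 2: the drop-out allowance.** 90/0.80 = 112.5, so 113. Multiplying instead gives 90 × 1.20 = 108. Neither is 120, which equals 90/0.75, a 25% loss. The discrepancy is on the safe side: 120 × 0.80 = 96 evaluable carriers give about 83% power within carriers.

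**Step 3: standard error of the interaction.** With 1:1 allocation in each stratum and SD 10 in both,

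SE = 10 × √(4/n_carriers + 4/n_non-carriers).

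With 120 carriers and 190 non-carriers at 20% loss there are 96 and 152 evaluable, so SE = 10 × √(4/96 + 4/152) = 2.61 points.

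**Step 4: power.** Power = Φ(interaction/SE − 1.96). The non-carrier effect has to be assumed, so three values are shown, each with 6 points in carriers:

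- Non-carriers gain 0: interaction 6; 6/2.61 − 1.96 = 0.34; power 63%.
- Overall effect is 4: with carrier share 120/310 = 0.387, the non-carrier effect is (4 − 0.387 × 6)/0.613 = 2.74; interaction 3.26; power 24%.
- Non-carriers gain 4: interaction 2; power 12%.

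**Step 5: vary carrier share and loss.**

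| Carriers | Loss | Evaluable carriers / non-carriers | SE | Non-carriers gain 0 | Overall effect 4 | Non-carriers gain 4 |
|---|---|---|---|---|---|---|
| 39% | 20% | 96 / 152 | 2.61 | 63% | 24% | 12% |
| 47% | 20% | 116 / 132 | 2.55 | 65% | 31% | 12% |
| 50% | 20% | 124 / 124 | 2.54 | 66% | 35% | 12% |
| 39% | 15% | 102 / 162 | 2.53 | 66% | 25% | 12% |
| 50% | 15% | 132 / 132 | 2.46 | 68% | 37% | 13% |

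The documents give only a ceiling for carriage. At an assumed 30% carriers and 20% loss, the three powers fall to 58%, 18% and 11%.

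**Step 6: what the test can detect.** With 80% power the detectable interaction is 2.80 × SE: 2.80 × 2.61 = 7.3 points in the first row and 2.80 × 2.46 = 6.9 in the last. Both exceed the whole 6-point effect assumed in carriers. The 95% CI half-width in the first row is 1.96 × 2.61 = 5.1 points.

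**The case against.** No primary inference depends on this calculation. SAP 5 bases primary inference on the primary endpoint in the ITT population, the 310 are sized on the main comparison, and Protocol 6.3 lists filaggrin as a predictor among the exploratory analyses. The text also says openly that the 90 are carriers compared between treatment groups. And by planning an interaction test on one outcome, SAP 7 already guards against presenting a significant result in carriers alone as prediction. All of this stands and limits the seriousness of the point. It does not remove the mismatch, because the Protocol gives the purpose of the carrier calculation as "In order to ensure that sufficient power is available for the planned sub group analysis", and the analysis planned is the interaction.

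A reader might infer more than the documents support:

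- **That interaction power is 24% to 63%.** Both ends rest on an assumed non-carrier effect, a 39% carrier share and 20% loss. The 4 points used for the lower end is described as a minimum relevant difference, not as the expected effect. Other reasonable choices give about 12% to 68%.
- **That the test could hardly ever succeed.** Power of 63% to 68%, when non-carriers gain nothing, is inadequate but not negligible.
- **That 145 should be 150.** The t-test gives 120/0.80 = 150, but the normal approximation gives 118/0.80 = 147.5, so 148, about 2% above 145. At 145 carriers the within-carrier power is still about 89%. This is not a clear error.
- **That 20% loss contradicts the main trial's 15%.** Protocol 12.3 lets families opt out of the genetics study, and Protocol 12.2 requires a saliva or cheek sample. A higher loss for this analysis is plausible, although the reason is not given.

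**Conclusion.** The point holds and should be fixed, but it does not threaten the primary result. The figures of 90, 120 and 145 concern the treatment difference within carriers, and as written they are offered as power for a subgroup analysis whose named test is the interaction. Interaction power is about 12% to 68% for non-carrier effects of 0 to 4 points, 39% to 50% carriers and 15% to 20% loss. No scenario examined with a zero or positive non-carrier effect reaches 80%. The calculation assumes 6 points in carriers, SD 10 in both strata, balanced arms within strata, loss unrelated to genotype, and a normal approximation. An opposite (harmful) effect in non-carriers would raise the power, but the documents give no reason to plan on one.

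Separately, the statement "Allowing for a 20% drop out means that 120 children would need to carry the gene mutation" does not follow from 90, which becomes 113. This is a minor and conservative discrepancy.

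**What to change.** In Protocol 12.4 and SAP 7:

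1. State that the 90-child figure is power for the treatment difference within carriers, and not for the interaction.
2. Give interaction power conditional on the assumed non-carrier effect and carrier share, for example the table above, together with the detectable interaction of about 7 points.
3. Report the interaction estimate with its 95% CI alongside the p-value.
4. State that a non-significant interaction is not evidence that filaggrin does not matter.
5. Replace 120 with 113, or state the loss rate that gives 120 (25%).

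The cost is wording only. No extra children are needed and the primary analysis is unchanged, but a less favourable power has to be put on record for the subgroup.

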13. TRIAL ADMINISTRATION

13.1 Trial personnel

This study will employ a part-time trial manager (60% fte) and 4 part-time research nurses (60% fte). Two MCRN-funded research nurses are also working part-time on the study (London and Lincolnshire). All staff will be supervised by [name] at the University of Nottingham, although the research nurses employed at the other recruiting centres will report directly to the Principal Investigators for those centres. Water engineering aspects have been sub-contracted by UK WTA to MG Heating, Newport for all installations on the Isle of Wight. Kinetico Ltd, Southampton, are working on behalf of UKWTA, facilitating installations and engineering support on the mainland. Each company has a dedicated water engineer co-ordinator (who is a member of the Trial Management Group) and who will arrange and supervise visits by their own water engineers to participants homes.

In addition, a consumer panel has been convened consisting of 5 service users with experience of living with eczema. [name] acts as the consumer panel representative on the Trial Steering Committee. Copies of the participant information sheets, symptom diaries and publicity material have been shown to the panel of service users prior to submission for ethical approval. The panel members shared these documents with children with eczema aged 4 and 13 years.

13.2 Roles & responsibilities

The Chief Investigator will have overall responsibility for the design, maintenance and delivery of the trial, and will serve as the study guarantor to sponsors, funders and journals.

The Trial Manager will be responsible for all aspects of the day-to-day running of the trial

The research nurses will be responsible for identifying and recruiting suitable participants, for conducting skin assessments and liaising with the local engineers over visit dates and times (prior to randomisation). Since research nurses are responsible for conducting the blinded outcome assessments, contact after the initial recruitment interview will be kept to a minimum. Subsequent telephone follow-up will be conducted by the trial manager or study support staff at the co-ordinating centre in Nottingham.

The Clinical Trials Support Unit (University of Nottingham) will provide data management for the trial. This will include a web-based randomisation service (with telephone backup), database design, data entry and central data monitoring.

[name] at the MRC Clinical Trials Unit in London will prepare an analysis plan prior to analysis.

13.3 Conflicts of interest

None

13.4 Trial Organisation & administration

The trial is funded by the NHS Health Technology Assessment Programme. It is sponsored by the University of Nottingham, and will be managed and co-ordinated from the Centre of Evidence Based Dermatology in Nottingham. Data management will be conducted through the Nottingham Clinical Trials Support Unit. Statistical analysis will be over-seen by [name] at the MRC Clinical Trials Unit in London, and conducted by a junior statistician employed at the same trials unit.

Membership of the Trial Steering Committee (TSC) and Trial Management Group (TMG) have been documented at the beginning of this document.

The Trial Steering Committee will meet at least once a year and will provide overall supervision of the trial on behalf of the trial sponsor.

The Trial Management Group will meet more frequently and will be responsible for the day-to-day management of the trial. Members of the TMG will report to the TSC at their meetings.

Since this trial involves the use of a commonly available domestic water softening unit (and does not involve a medicinal product) we do not anticipate the need for a Data Monitoring Committee.

13.5 Trial Timetable and Milestones

| | 6 months | 26 months | 4 months | 3 months | 4 months |
|---------------------|-----------------------------|--------------------------|--------------------------|--------------------------|-----------------------------|
| | 1 Sep 06 to 28 Feb 07 | 1 Mar 07 to 31 May 09 | 1 Jun 09 to 30 Sep 09 | 1 Oct 09 to 31 Dec 09 | 1 Jan 10 to 31 Apr 10 |
| Trial set-up* | | | | | |
| Training** | | | | | |
| Recruitment | | | | | |
| Follow-up | | | | | |
| Data checking | | | | | |
| Database locked | | | | 31 Dec 09 | |
| Analysis / write up | | | | | |
| MREC L | REC and R&I |) approval | | | |

^{*} Trial set-up will include the establishment of sponsorship agreement; preparation of trial procedures and CRF's; application for ethics and R&D approvals; purchasing equipment and publishing the protocol. Research nurses employed at each site and the study engineers will be identified during the 6-month set-up period.

13.6 Unblinding of participants

This is a single-blind study, in which unblinding of the study participants is not relevant. However, attempts will be made to ensure the continued blinding of the research nurses and the trial statistician. If any of the research nurses feel that blinding may have been compromised at any time, this will be logged accordingly.

14. ETHICS

14.1 Statement of confidentiality

Any data collected as a result of this trial will be treated as confidential. Participants will be identified by unique reference number and initials wherever possible. It is necessary for participants' name and contact details to be released to the co-ordinating centre, but this will not happen until fully informed consent has been taken.

14.2 Data protection

Data will be stored in accordance with the Data Protection Act. Investigators will retain patient records and CRFs in easily retrievable but secure form.

The Chief/Principal investigator will ensure that CRFs and other study documentation relating to their participants are kept in a locked departmental filing cabinet. Completion of, and access to the CRFs will be restricted to those personnel approved by the

^{**} Training of Principal Investigators, Water Engineers and Research Nurses, including awareness of GCP.

Chief/Principal investigator.

15. ADVERSE EVENT REPORTING

This trial involves the use of a commonly available domestic water softening unit with provision for mains drinking water during the time when the water softening unit is installed. This being the case, we do not anticipate any adverse events or adverse reactions of any relevance to the trial. As a result adverse event data will not be routinely collected. Events of particular relevance such as plumbing difficulties, floods or difficulties with the units will be logged and reported to the MREC and relevant R&D departments annually.

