2.3 Benefit / risk assessment

This is very low risk trial as the intervention is non invasive with no known clinical side effects. Participants simply receive softened water for bathing and washing of clothes. Drinking water will remain unchanged.

The water softening units will be installed by a qualified water engineer according to the Code of Practice produced by British Water.

The unit to be used is a generic version of a commercially available unit which has been encased in a generic outer box in order to prevent commercial advantage for any individual water softener supplier. Ion-exchange technology is well understood and widely used throughout the world.

Possible benefits to trial participants, in addition to improvement in eczema symptoms, include reduced scaling of water appliances, reduced soap / cleaning product consumption and reduced energy consumption.

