5. INTERVENTIONS

5.1 Treatments to be compared

Ion-exchange water softening units will be compared with usual care. Ion exchange water softening is a scientifically defined, understood and described process using a synthetic polystyrene resin in which primarily the divalent cations (positively charged), calcium and magnesium found in domestic water supplies, are replaced by the monovalent cation, sodium, from common salt. The water softener used in the study has two cylinders of resin which are used alternately. A control valve ensures that when the resin capacity of one cylinder is exhausted it automatically switches the water flow to the second cylinder and, using common salt, regenerates the first to be ready for use when the second is exhausted. Ion-exchange water softening units typically reduce the water hardness to practically zero¹.

All units will be installed in the child's principal residence and salt will be supplied for the duration of the trial. Standard procedure will be to soften all water in the home, and provide mains drinking water through an extra (faucet-style) tap installed at the side of the kitchen sink. Participants will be given the opportunity to opt out of having this

¹ By contrast, physical water conditioners affect the behaviour of calcium in water but they do not remove it. The process by which they have this effect is not fully understood scientifically and so their design is empirical. Whether or not Physical Water Conditioners have a beneficial effect on eczema is a question for future study once proof of principle has been tested using established ion-exchange technology.

separate, mains drinking water tap if they prefer.

Apart from having a unit installed in the home, participants will continue with their usual eczema treatments in the usual way and will be asked to bathe / wash their clothes according to their usual practice. The units will meet all necessary quality standards, and will be installed by a trained water engineer according to British Water's code of practice.

The water softeners to be used in this trial will be supplied and paid for by a consortium of representatives from the water treatment industry, co-ordinated through their Trade Association. The units will be encased in an unmarked box in order to prevent the possibility of commercial advantage to any particular company. Similarly, unmarked salt will be supplied for use during the trial.

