7.1 Inclusion criteria

- Children aged 6 months to 16 years at baseline, with eczema as defined by the UK refinement of the Hanifin and Rajka diagnostic criteria ¹⁴.
- Eczema present at time of assessment (minimum SASSAD score of 10).
- Baseline water hardness of >200 mg/L of calcium carbonate.
- Home suitable for the installation of a water softening device (as assessed by water engineer)

Only one child will be enrolled per family. The choice as to which child becomes involved will be made by the parents and children involved, taking into account the inclusion criteria above.

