9.1.2. Treatment diaries

Diaries will be used to capture:

- i. the number of days when active topical treatment (topical corticosteroids, tacrolimus or pimecolimus) is applied
- ii. whether or not treatment has needed to be "stepped up" if so, in what way and for how many days ("stepping up" treatment will be defined in advance by the parents in consultation with the research nurse)
- iii. daily global assessment of disease activity by child and parents
- iv. nights away from home

³ Target lesion nominated by research nurse in discussion with the child/parents.

- v. health service resource use
- vi. personal costs associated with the eczema
- vii. whether or not the accelerometers have been worn (weeks 1 and 12).

Items i) and ii) above will be used to calculate the number of totally controlled weeks (TCW) and well controlled weeks (WCW) during the study. Diaries will also be used to remind participants to check the salt levels in the machine and to return a sample of the water for testing in the laboratory every week.

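### The rule not to collect adverse events rests partly on mains drinking water being provided, yet families may decline the mains tap, tap status is not a listed data item, and the SAP has no by-arm summary of clinical adverse events

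*Combined protocol and SAP*

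**What the plan says.** Protocol section 15 argues in three steps. The unit is an ordinary domestic appliance, used with "provision for mains drinking water during the time when the water softening unit is installed". From this it concludes: "This being the case, we do not anticipate any adverse events or adverse reactions of any relevance to the trial". It then states: "As a result adverse event data will not be routinely collected". Events of particular relevance are to be logged and reported once a year to the ethics committee and R&D departments. Every example given is a plumbing or unit problem.

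Section 2.3 makes the same assumption without qualification: "Drinking water will remain unchanged".

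Section 5.1 describes the installation: "Standard procedure will be to soften all water in the home, and provide mains drinking water through an extra (faucet-style) tap". It then adds: "Participants will be given the opportunity to opt out of having this". The sentence is interrupted by a footnote and goes on to name the separate mains tap as the item that may be declined.

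Section 7.1 admits "Children aged 6 months to 16 years at baseline". Section 13.4 foresees no data monitoring committee, because the unit is commonplace and no medicinal product is involved. Among other items, the diary in section 9.1.2 records "health service resource use", which section 11.1 uses for costing.

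**The concern.** Section 15 presents the absence of adverse event collection as following from facts about the intervention. One of those facts, the mains drinking supply, is optional under section 5.1. The decision therefore rests partly on a condition that a family can remove, and neither section 15 nor section 2.3 allows for this.

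Two gaps make this more than a wording conflict. First, from the data items the documents list, the homes that declined the tap could not be picked out afterwards. Second, the SAP plans no summary of clinical adverse events in either arm. The trial will report on effectiveness and cost-effectiveness, while the statement in section 2.3 that the intervention has no known side effects would remain an assumption.

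**Working it through.** The plan gives no figure to reproduce here. The check compares sections, followed by two short calculations for scale.

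**1. The drinking-water premise**

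| Place | What it implies |
|---|---|
| Protocol 2.3 | Drinking water is unchanged, with no exception |
| Protocol 15 | Mains drinking water is provided throughout installation |
| Protocol 5.1 | The whole supply is softened as standard; mains water comes from an extra tap; families may decline that tap |

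The first two statements hold as written where the tap is fitted. Where it is declined, section 5.1 does not say what mains supply remains, so the premise may not hold.

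**2. Are those homes identified?** Neither tap status nor the child's drinking source appears in the nurse visits (9.1.1), the diary items (9.1.2), Table 1 or the engineer's visits (9.5). In the SAP, neither appears among the per-protocol criteria (section 5), the covariates and baseline characteristics (6.2) or the compliance measure (9.2).

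**3. What does the SAP summarise by arm?** Its sections run from 1 to 12 with no safety analysis. The nearest items are withdrawals with reasons by allocation (9.3), SASSAD (10.1), and controlled weeks, which count stepped-up treatment days (8.3 and 10.2).

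**4. What collection would have shown.** With zero events in n children, the one-sided upper 95% bound on risk is 1 − 0.05^(1/n).

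- Group A, n = 155 (section 3): 1 − 0.05^(1/155) = 1.9%.
- With the 15% attrition of section 10.2, 155 × 0.85 = 131.75, about 132: 1 − 0.05^(1/132) = 2.2%.
- Homes that decline the tap: the rate is not given, so these are assumptions, before attrition. At 10% (about 15 children) the bound is 18.1%; at 20% (31 children), 9.2%; at 50% (about 78 children), 3.8%.

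**5. Does softening change the water?** Section 5.1 says calcium and magnesium are exchanged for sodium. Each 100 mg of hardness as calcium carbonate is 1 mmol of divalent cation, replaced by 2 mmol of sodium, or 46 mg. Entry requires more than 200 mg/L (section 7.1).

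- Complete removal at that limit: 200 × 0.46 = 92 mg/L of sodium gained.
- Residual hardness of 20 mg/L, above which section 5.2 refers a sample to the engineer: (200 − 20) × 0.46 = 82.8, about 83 mg/L.

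This shows only that softened water differs from mains water. The documents give no sodium benchmark, so no consequence can be drawn from the figure.

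**The case against.** The strongest reply is that omitting adverse event collection was a reasoned choice for a common, non-medicinal household device. That half of the rationale survives the opt-out. An offered tap that a family declines might also still count as provision. The conflict with the unqualified statement in section 2.3 remains.

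Several stronger readings are tempting but not supported:

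- A reader might infer that children in opt-out homes drank softened water. Section 5.1 describes the standard procedure, not the plumbing where the tap is declined, and no opt-out rate is given. The group could be empty.
- A reader might infer that children are unmonitored and that nothing unfavourable is compared by arm. Nurses see them at 4, 12 and 16 weeks, there is an 8-week call, withdrawals with reasons are tabulated by allocation, and eczema worsening is compared. What is missing is clinical adverse events and drinking source.
- A reader might infer that only technical events can be logged. Section 15 introduces its list as examples.
- A reader might infer that existing diary data would answer the question. The diary lists resource use without saying that a reason for contact is recorded.

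Two further points stand. Installation forms and case report forms are not reproduced, so tap status might be captured there. Parents are unblinded, and the SAP (footnote to section 3.2) dropped a parent-reported global rating partly because of bias. Any event table would share that weakness.

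**Conclusion.** The conflict between sections 2.3, 5.1 and 15 is real and visible in the current text. In homes that decline the tap, one of two stated premises for not collecting adverse events may not hold. The listed data items do not identify those homes, and the SAP has no by-arm summary of clinical adverse events.

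The size is limited. With collection, an absence of events would have bounded the Group A risk at roughly 2%; without it, no bound is available. For opt-out homes alone the bound would be about 9–18% if 10–20% declined, so collection could describe that group but not settle anything about it. These bounds assume that events would be reported completely.

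The documents do not support a conclusion that softened water harms children or that any child drank it. The primary analysis and sample size are untouched. This is an inexpensive improvement that should be made, not a threat to the main result.

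**What to change.** 1. Reconcile protocol sections 2.3, 5.1 and 15 on drinking water. Whether the tap should be required is for the investigators; no view is taken here.
2. Record at installation whether the mains tap was fitted or declined.
3. Revise section 15 so that unfavourable health events, and the reason for unplanned health-care contacts, are collected in the same way in both arms. Use the existing diary and the 8-week call by the unblinded trial manager, which keeps the questions away from the blinded nurses.
4. Add one descriptive SAP table by arm for weeks 0–12 covering these events and contacts, with logged unit and plumbing events per installed home, and show tap-declined homes separately. Group B has no unit in that period, so the tap-declined and unit rows are Group A counts, not between-arm comparisons.

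The cost is one tick-box, one or two diary and telephone questions, and one table, with no new visit, staff or sample size. The drawback is that unblinded parents may report differently by arm, so the table should be labelled descriptive and carry no test.
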